BMI is a widely used as an index of nutritional problems. In a meta-analysis which included 2.88 million people, the optimal BMI for overall survival was found to be 25-30 kg/m² (Flegal, 2013; Dixon, 2014 ; Pan, 2012). Rapid weight loss is a strong indicator for health and functional decline. Such a weight loss, especially with low BMI values, usually mandates investigation in order to eliminate the cause or to limit its effect. A use of an automatic e-mail alert system was found to improve screening rate of malnourished patients in hospital (Giovannelli, 2014).

Correlation between death and HbA1c% is U-shaped, with increased mortality under a 6.5% level in patients taking two antidiabetic medicines (Currie, 2010). Among these patients, the optimal HbA1c% values of for survival were 7.5-8%. A substantial proportion of older adults with diabetes were found by Lipska et al. (2015) to be potentially overtreated.

Correlation between death and cholesterol is also U-shaped (Iso, 1989). Hypocholesterolemia is defined as cholesterol below 160 mg% and predicts increased mortality and morbidity (Hazzard's, p. 1341). We found no interventional study for this situation in the scientific literature.

In our experience, Email alerts to doctors, regarding an over-tight control of specified diabetic patients by sulphonyl-urea medicines was followed by a reduction (from 3% to 1.8%) in

mortality comparing to a previous-year matched control group (unpublished observations). While this result was not statistically significant, it encouraged us to try this large scale interventional clinical trial. It also served us in assessing the size of the study population needed.

Objectives:

This study aims to determine whether reminding physicians and nurses about too low values of weight (as BMI), glucose (as HbA1c%) or cholesterol (as total serum cholesterol) improves survival and health of people older than 75 years.

Study Hypotheses:

A. Main Study Hypotheses:

1. Compliance: Sending the intervention letter will cause a positive change in the relevant index (a rise in BMI, HbA1c%, or cholesterol, respectively).
2. Health effect: Sending the intervention letter will cause a lower mortality rate in each study group compared to control groups, within a year.

B. Other Study Hypotheses: compared to control groups, sending the intervention letter will cause improvement in morbidity and in secondary measures (see below).

And in detail:

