0. Preparations:

A pre-trial email will be sent to the primary physicians on behalf of the district managements in order to inform about the trial. The text is provided in appendix No. 4. Feedback regarding receiving of the letter (full email boxes etc.) will be collected. Primary physicians would be able to choose to refrain from participating.

1. Finding the participants:

A. By using the Clalit health services computer system; an Excel table will be created; which will include these fields: Identity number; Name; Age; Sex; Clinic name; Primary physician name; Primary physician's email address; Nurse in charge at the clinic; email address of that nurse; Last BMI value of the last year; First BMI value of the previous year; Existence of a dietician visit on the last year; Last total cholesterol level; Whether dispensing of a cholesterol lowering medicine was recorded during the last 2 months; Name of (the last) cholesterol lowering medicine dispensed - with dose and quantity; Whether dispensing of a diabetes medicine was recorded during the last 2 months;

¹ AND as intersection

Name of (the last) diabetes medicine dispensed - with dose and quantity; Whether diagnosed with myocardial infarction; Whether diagnosed with brain infarction; Whether diagnosed with any cardiovascular disease.

B. Participants for each separate inclusion group, according to the criteria above, will be identified. At this stage, a new list will be created, where the people who don't fit any of the criteria will be excluded. Some of the participants may fit more than one criterion. Hence 7 subgroups are created:

- A) Patients that fit only alert 1. (Significant weight loss without dietitian assessment)
- B) Patients that fit only alert 2. (A potentially too tight medicinal diabetes treatment)
- C) Patients that fit only alert 3. (A potentially too tight medicinal cholesterol lowering)
- D) Patients that fit both alert 1. and alert 2.
- E) Patients that fit both alert 1. and alert 3.
- F) Patients that fit both alert 2. and alert 3.
- G) Patients that fit all alerts: 1. , 2. and 3.

C. Population size: According to 11.2014 there are about 5000 patients that fit these criteria at North district and a similar number at the South district, totaling ~ 10,000. This provides a sufficient statistical power to examine the effect on the main hypotheses. (We used Pearson χ^2 test, assuming a 3% to 1.8% decline in death rates, as observed in a similar setting).

2. Randomization:

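### Section 1.C claims sufficient power for the main hypotheses, but its single calculation covers only a pooled mortality comparison

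*Combined protocol and SAP*

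**What the plan says.** Study Hypotheses, part A, lists two main hypotheses. The first, on compliance, reads "Sending the intervention letter will cause a positive change in the relevant index (a rise in BMI, HbA1c%, or cholesterol, respectively"). The second, on health effect, reads "Sending the intervention letter will cause a lower mortality rate in each study group compared to control groups, within a year".

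Study procedures and methods, 1.C, counts about 5,000 eligible patients in each of two districts, about 10,000 in all, and concludes: "This provides a sufficient statistical power to examine the effect on the main hypotheses". It names the Pearson chi-square test, "assuming a 3% to 1.8% decline in death rates, as observed in a similar setting". It gives no power figure and no required sample size. The setting is described in Background, where an email alert about over-tight control of "specified diabetic patients by sulphonyl-urea medicines was followed by a reduction (from 3% to 1.8"%) in mortality against a matched group from the previous year. Background adds that this was unpublished and not statistically significant.

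On the groups, 1.B says "Participants for each separate inclusion group, according to the criteria above, will be identified" and "Some of the participants may fit more than one criterion". It gives neither the size of any alert group nor the extent of overlap. Under 0. Preparations, "Primary physicians would be able to choose to refrain from participating". Outcome analysis compares the study arms by chi-square or Fisher's exact test for categorical variables and by t-test or Wilcoxon for continuous ones, at P < .05. It does not say whether mortality is tested pooled or by alert.

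**The concern.** The sufficiency claim is wider than the calculation beneath it. The calculation takes the total population and one pair of death rates, so it describes a single comparison of all intervention patients with all controls. Hypothesis 2 as written asks about each study group, and each alert group is smaller than the total unless every patient meets that alert. Hypothesis 1 concerns a shift in BMI, HbA1c% or cholesterol, for which a death-rate calculation carries no information.

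What is at stake is interpretation. A non-significant mortality result for one alert would be read against a statement that the study had sufficient power, and could be taken as evidence that the alert does not work. The plan has shown no such power for a single alert.

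**Working it through.** **Inputs from the documents.** Total about 10,000 (1.C); 1:1 allocation (2. Randomization), hence about 5,000 per arm; one-year mortality 3.0% against 1.8% (1.C); significance level 0.05 (Outcome analysis). Sidedness is not stated; two-sided is assumed unless marked.

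**Formulas** (chi-square, pooled null variance, n per arm, p̄ = 0.024):
- Power = Φ{[d − z(α)·√(2p̄(1−p̄)/n)] / √([p1(1−p1)+p2(1−p2)]/n)}, where d = p1 − p2.
- n for 80% power = {[z(α)·√(2p̄(1−p̄)) + 0.842·√(p1(1−p1)+p2(1−p2))] / d}².

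**1. The plan's own claim, pooled.** With n = 5,000 both standard errors are about 0.00306. Power = Φ[(0.012 − 1.96 × 0.00306)/0.00306] = Φ(1.96) = 97.5%. The plan prints no figure to match, but sufficient is a fair word for this comparison at these inputs.

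**2. Size needed in any one group at the same rates.** Two-sided: [(0.4242 + 0.1820)/0.012]² gives 2,553 per arm, or 5,106 patients. One-sided: [(0.3560 + 0.1820)/0.012]² gives 2,011 per arm, or 4,022 patients.

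**3. Can the total supply it?** Two non-overlapping groups of 5,106 need 10,212, more than 10,000, so at most one could reach that size. All three need 3 × 5,106 = 15,318 group memberships, an average of at least 15,318/10,000 = 1.53 alerts per patient. One-sided, two groups would fit (8,044) but three would not without overlap (12,066, or 1.21 alerts per patient).

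**4. Power in one group. Sizes are assumed, since none is given.**

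| Patients in group | Two-sided power | One-sided power |
|---|---|---|
| 3,333 (equal third, no overlap) | 62% | 73% |
| 5,000 | 79% | 87% |

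At 3% control mortality, the smallest drop detectable with 80% power is 0.88 points pooled and 1.45 points in a group of 3,333. The plan expects 1.2.

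**5. Sensitivity to control mortality (assumed 5%), group of 3,333.** With the risk ratio kept at 0.60 (5% against 3%), power is 84%. With the drop kept at 1.2 points (5% against 3.8%), it is 39%. The direction depends on which quantity carries over.

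**6. Limits of the pooled figure.** Assumed opt-out losses of 10%, 20% and 30% leave 96%, 94% and 91%. Dilution matters more. If the 1.2-point drop occurs in two thirds of patients, the pooled rates are 3.0% and 2.2% and power is 71%; if in one third, they are 3.0% and 2.6% and power is 23%.

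**7. Hypothesis 1.** The documents give no expected shift, standard deviation or share measured, so power cannot be computed. For scale, the standardized difference detectable with 80% power is (1.96 + 0.842)·√(2/n): 0.10 SD for 3,333 patients if all are measured (n = 1,667) and 0.14 SD if half are.

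**The case against.** The strongest reply is that only one comparison was ever intended. The randomization section speaks of an intervention group and a control group, Outcome analysis refers only to the arms of the study, and the text is a translation in which the phrase about each study group could be loose. On that reading the calculation fits hypothesis 2. This has some force, because the plan never says whether testing is pooled or per alert. But the word each, the plural control groups, the three separately defined alerts and the alert-specific outcomes all favour the per-alert reading. On either reading hypothesis 1 remains uncovered.

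A second reply is that 3% may be too low for some alerts: Background describes rapid weight loss as a strong sign of decline and low cholesterol as predicting higher mortality. At a constant risk ratio, higher mortality would raise per-alert power. That stands as a possibility, but no rate is given, and at a constant absolute drop the effect reverses.

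In the other direction, a reader might infer that the per-alert tests are underpowered, or that the trial is too small. The documents do not support that: a large alert group, heavy overlap or higher control mortality at the same risk ratio could give adequate power. Nor does any passage require all three alerts to be significant together. For hypothesis 1 the gap is one of documentation; samples of this size may well suffice for a continuous index.

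**Conclusion.** The concern holds as a mismatch between claim and calculation. Sufficiency is shown for one pooled mortality comparison: about 97% power, resting on 3.0% against 1.8%, 5,000 per arm, two-sided 0.05, no opt-out and the effect present across alerts. Those rates come from sulphonylurea-treated diabetic patients and have no stated counterpart for the BMI or cholesterol alerts.

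For hypothesis 2 as written, sufficiency is not demonstrated: about 5,106 patients are needed per group against group sizes that are not reported. The 62% figure is illustrative and depends on assumed equal thirds. For hypothesis 1 there is no calculation, which says nothing about whether power is low. The wording should be fixed; the design does not depend on it.

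**What to change.** In 1.C, limit the claim to the pooled comparison, for example: *About 10,000 patients (about 5,000 per arm, before physician opt-out) give about 97% power for the pooled one-year mortality comparison, assuming 3.0% versus 1.8% and two-sided 0.05; the rates come from an unpublished comparison in sulphonylurea-treated diabetic patients.* Add that pooled power falls if the letter works in only some alerts.

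Then make hypothesis 2 agree with it, in one of two ways:
- Name pooled mortality as the powered test. Report per-alert mortality differences with 95% confidence intervals and each group's minimum detectable difference once alert-group counts are extracted.
- Keep hypothesis 2 per alert, and state each group's size, assumed control rate and power.

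State the choice in Outcome analysis too. Do not extend the claim to hypothesis 1 unless a separate calculation is given (index, expected shift, standard deviation, share measured).

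The cost is a few sentences in 1.C, Study Hypotheses and Outcome analysis, and perhaps one count query; no extra patients. The downsides are that the stated per-alert power becomes less favourable and that, under the first option, the powered test is exposed to dilution.

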- a. Randomization aims to get an unbiased and equal division into an intervention group and a control group.
- b. Randomization will be via computer: by adding a column in the excel table, with the function =ROUND(RAND(),0). This means 1:1 randomization to 0 (control) or 1 (intervention letter).
- c. In order to avoid large differences in numbers of participants among the subgroups, the randomization procedure will repeat until the difference between control and intervention group is less than 2%.

3. The alert emails will be prepared and sent via "Mail Merge" (of Microsoft Word) to the primary physicians and to the nurses in charge at the same clinics. The templates to those emails are shown in the appendix. Technical problems (e.g. full mailbox of recipients) will be recorded and managed promptly (- days, hopefully), by the principal investigator.

4. Collecting outcome data: will be via the Clalit health services computer system. Data will include:

a. For all participants (control and trial groups), for the year that follows the intervention email:

1. Mortality (of any cause)
2. Days in stays (of any ward)
3. Number of stays
4. Number of physician visits
5. Number of nurse visits with symptoms
6. Number of all medicines dispensed
7. Medical expenses
8. Last BMI level and date
9. Last cholesterol level and date
10. Last HbA1c% level and date
11. Glucose levels of 70 mg/dL or less, and dates

b. For alert 1., for the year that follows the intervention email:

1. Recording of functional estimation by a nurse
2. Recording nutritional estimation by a nurse
3. Recording dietitian consultation

c. For alert 2. on the 3 months that follows the intervention email:

1. Whether a diabetes medicine was dispensed, and if so:
2. Name of diabetes medicine, dose and quantity

d. For alert 3. on the 3 months that follows the intervention email:

1. Whether a cholesterol lowering medicine was dispensed, and if so:
2. Name of medicine, dose and quantity

5. Data security: will be handled according to Clalit health systems procedures. The information will be saved in allowed secure servers only and will be available to authorized researchers only after their guidance and signing a non-disclosure commitment. When applicable, personal identification details will be omitted from the lists.

6. Outcome analysis:

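### The redraw rule is meant to balance the seven subgroups but stops on an arm difference whose level and denominator are unstated; one stratified draw would deliver the aim directly.

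*Combined protocol and SAP*

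**What the plan says.** All references are to the combined protocol and SAP, Study procedures and methods.

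- **Item 1 B** sorts eligible patients by which of the three alerts they meet: "Hence 7 subgroups are created", labelled A to G. No sizes are given. Item 1 C gives only the total: about 5,000 in the North district and "a similar number at the South district, totaling ~ 10,000".
- **Item 2 a** states the aim: "Randomization aims to get an unbiased and equal division into an intervention group and a control group".
- **Item 2 b** allocates "by adding a column in the excel table, with the function =ROUND(RAND(),0"), and adds: "This means 1:1 randomization to 0 (control) or 1 (intervention letter").
- **Item 2 c** gives a purpose, "In order to avoid large differences in numbers of participants among the subgroups", and a stopping test: "the randomization procedure will repeat until the difference between control and intervention group is less than 2" per cent.
- **Item 3** goes straight to the mail merge. No seed, log of draws or saved final list is described.

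**The concern.** The purpose and the stopping test in item 2 c refer to different things. The purpose concerns the subgroups, a word the plan defines only as A to G. The test compares control with intervention. Three things needed to carry it out are missing: whether the 2% applies to the whole sample or inside each subgroup, what it is a percentage of, and whether a failed draw means redrawing the whole list or only the failing subgroup. Two people following item 2 c could do quite different things.

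At stake is whether the procedure delivers the balance it was written for, and whether the final allocation can be reproduced and checked when outcomes are compared a year later.

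**Working it through.** **Inputs.** Total about 10,000 (item 1 C), seven subgroups (item 1 B), independent 1:1 allocation (item 2 b), threshold 2% (item 2 c). Subgroup sizes are not in the documents, so five splits are assumed:

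- S1: seven of 1,429 (total 10,003)
- S2: 2000/3000/3000/500/500/800/200
- S3: 1500/3500/3500/150/150/1150/50
- S4: 1000/3500/4000/200/200/1000/100
- S5: 1500/3500/4500/100/100/280/20

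**Step 1. The plan's own figure.** Item 1 C calls 10,000 sufficient, "assuming a 3% to 1.8% decline in death rates", without stating a power. With 5,000 per arm and two-sided 0.05 (sidedness assumed), the null standard error is √(2 × 0.024 × 0.976/5000) = 0.00306, and the alternative one is also 0.00306 after rounding. Then z = (0.012 − 1.96 × 0.00306)/0.00306 ≈ 1.96, a power of 97.5%. The statement is supported for one pooled comparison. The plan gives no figure for how often the 2% rule is met.

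**Step 2. Rule applied to the two arms.** With K ~ Binomial(n, ½), the chance that one draw passes is p(n) = P(|2K − n| < 0.02n). For n = 10,000, K must lie between 4,901 and 5,099, so p = 0.953. If 2% means each arm's share within 48–52%, p = 0.9999. If it means 2% of the smaller arm, p = 0.678.

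**Step 3. What this leaves inside the subgroups.** Without the arm rule, the chance that at least one subgroup is 2% or more out is 1 − ∏p(nᵢ).

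- S1: 1 − 0.541⁷ = 1 − 0.0136 = 98.6%.
- S3: 1 − (0.546 × 0.757 × 0.757 × 0.193 × 0.193 × 0.502 × 0.112) = 1 − 0.00066 = 99.9%.

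In 200,000 simulated draws, counting only those that pass the arm rule (2% of the total), the figure is about 98.6% for S1 and 99.8% or more for S2 to S5. The arm rule therefore changes almost nothing. The remaining imbalance is that of plain coin tossing, with a 95% limit of about 1.96/√n: 6.2% for n = 1,000, 14% for 200 and 20% for 100.

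**Step 4. Rule applied within each subgroup.** Expected draws are 1/∏p(nᵢ) if the whole list is redrawn until all seven pass, and Σ 1/p(nᵢ) if each subgroup is redrawn separately.

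| Split | Whole list, 2% of total | Whole list, 48–52% share | Separate, 2% of total |
|---|---|---|---|
| S1 | 74 | 2.5 | 13 |
| S2 | 470 | 11 | 19 |
| S3 | 1,500 | 130 | 26 |
| S4 | 3,700 | 50 | 31 |
| S5 | 11,300 | 246 | 39 |

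An odd-sized subgroup cannot differ by less than one patient. Since 1/49 = 2.04%, an odd-sized subgroup of 49 or fewer can never pass if 2% means 2% of the subgroup total.

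**Step 5. Cost of the imbalance.** In a subgroup of 1,000 with 3% v 1.8% mortality, the Step 1 formula gives a power of 23.6% at 500/500. At 470/530 it gives 24.1% if control is the smaller arm and 22.9% if it is the larger. Relative information at 45/55 is 4 × 0.45 × 0.55 = 0.99.

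**Step 6. A stratified half split.** It leaves a difference of at most 1 patient per subgroup, so at most 7 of 10,000 (0.07%) overall, in one draw.

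**The case against.** The strongest reply is that item 2 c means the two arms. Item 2 a sets equal division into two arms as the aim, the stopping test compares exactly those two, and the text is a translation. On that reading the rule meets its purpose. This remains possible, but it needs a meaning of the word that the plan gives nowhere else, and the denominator would still be unstated.

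It can also be said that the mortality hypothesis concerns the three alerts rather than A to G, and that larger sets are better balanced. That is fair. Under S3 the three alert groups hold 1,850, 4,850 and 4,850 patients, with 95% limits of about 1.96/√n = 4.6%, 2.8% and 2.8%. Those limits still exceed 2%, but the gap is small.

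Three stronger readings are tempting and are not supported:

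- **That the rule is unworkable.** This needs a strict reading and sizes the documents do not give. Redrawing each subgroup separately takes tens of draws, and thousands can be automated. No small odd-sized subgroup is shown to exist.
- **That unequal counts invalidate or bias the comparison.** The redraw looks only at counts and treats the arms symmetrically, so each patient keeps a chance of ½. The tests named in item 6 do not need equal arms.
- **That the recorded arm will not match the letters sent.** The plan does not say the RAND() column stays live. That is an inference from silence, and repeating until a condition is met suggests one accepted draw.

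**Conclusion.** The point holds as a mismatch between aim and method. On the plain reading of the word subgroups, the arm-level rule accepts about 95% of draws (2% of the total) and leaves at least one of A to G 2% or more out in about 99% or more of them. That result does not depend on one chosen split: it holds for seven equal subgroups and for four unequal splits, all with seven non-empty subgroups. Applied within subgroups, the rule can mean anything from a few draws to thousands, or an impossible target, depending on sizes and definitions the plan does not supply.

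The consequence is modest. There is no bias and almost no loss of power, and the precision gained by stratifying the pooled test is small. The case for change is that a simpler procedure delivers the stated aim exactly, can be reproduced, and costs next to nothing. The missing step to fix the allocation is a gap to close, not a demonstrated error.

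**What to change.** Replace items 2 b and 2 c with one stratified draw. Within each of the seven subgroups, sort once by a seeded random number, assign half to intervention and half to control, and decide an odd last patient by coin. Drop the redraw rule. SAS 9.2, already named in item 6, can do this.

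Stratify the pooled mortality test by the seven subgroups (for example Cochran–Mantel–Haenszel), so that the analysis matches the allocation.

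Save the allocation as fixed values, with the seed, before the mail merge in item 3, and use that same file for both mailing and analysis.

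The cost is a few lines of code and a wording change to items 2 b, 2 c and 6, made before mailing. No extra patients or data are needed.

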Reducing numbers of hospital stays and days of stays, numbers of physician and nurse visits with records of symptoms, number of dispensed medicines, medical expenses; in the HbA1c% intervention - reduced number of dispensed anti-diabetes medicines and reduced rate of measuring glucose levels of 70 mg/dL or less ; in the cholesterol intervention - reduced number of dispensed anti-cholesterol medicines.

Increasing rate of weight measuring, BMI level, HbA1c% measuring, HbA1c% level, cholesterol measuring, cholesterol level; in the BMI intervention - percentage of patients evaluated by a nurse and counseled by a dietician.

Methodology:

Briefly: This prospective, randomized controlled trial, will compare BMI, HbA1c% and cholesterol values, rate of death, number of stays, days of stays, numbers of physician and nurse visits with records of symptoms such as "weakness", "dizziness" and total medical expenses of patients 75 years and older that their clinic staff will receive the email concerning them, versus patients that such email concerning them will not be sent. The trial has 3 different alerts: 1. An alert about a significant drop in BMI; 2. An alert about low HbA1c% level in patients treated with diabetes medicines; and 3. An alert about hypocholesterolemia in patients treated with cholesterol-lowering medicines.

Recruiting and inclusion criteria: 75 years and older at the beginning of the trial, clients of Clalit health Services at the North and the South districts, which will be identified thru the computer system (BO) as having one or more of the following:

For alert no. 1: A drop in BMI of 2 Kg/m² or more during the last two years and¹ a BMI lower than 23 Kg/m² and¹ no dietician counseling during the last year.

For alert no. 2: HbA1c% of 6.5% or less and¹ dispensing diabetes medicines during the last 2 months.

For alert no. 3: Total cholesterol less than 160 mg/dL and¹ dispensing cholesterol-lowering medicines during the last 2 months.

Exclusion criteria:

General: Clients that an email address of their physician or nurse is not found.

For alert no. 3: Clients with a diagnosis of myocardial infarction, ischemic heart disease, transient ischemic attack or cortical cerebrovascular accident.

Study schedule:

Sending the alerting mails will be done in one-session during 2015.

Collecting the data will be done after one year.

Publishing the main results will be done within another year at the latest (2017).

Study procedures and methods:

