Categorical variables will be shown as frequencies and percentages. Continuous variables will be shown using standard distribution indices (e.g. average, standard deviation, median, etc.). Differences between the arms of the study will be examined using Chi-square test (or Fishers' exact test) for categorical variables and T-test (or Wilcoxon two sample test) for continuous variables. The statistical processing will be performed using Excel or SAS 9.2 software and will be statistically significant if $P < .05$.

7. Ethical issues of the trial:

A waiver of the requirement to obtain a signed informed consent from participants is requested with the following reason: There is no contact with the patients, only unsheathing their existing data.

A waiver of Form 11 is requested with the following reason:

The family physician will be the one who would get the alert related to this trial in the first place.

Appendixes:

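### Does writing to staff who care for both arms leave the trial unable to answer its own objective?

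*Combined protocol and SAP*

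**What the plan says.** The Objectives section opens: "This study aims to determine whether reminding physicians and nurses about too low values of weight". Taken alone, that describes an effect on clinicians' practice in general.

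The rest of the protocol is narrower. The Methodology compares patients whose clinic staff are emailed about them "versus patients that such email concerning them will not be sent". Main hypothesis 2 reads: "Sending the intervention letter will cause a lower mortality rate in each study group compared to control groups, within a year". Main hypothesis 1 is likewise about sending the letter.

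Under Study procedures, item 2 allocates each row of the patient table by a computer coin flip, with no grouping by clinic or physician. Item 3 sends the letters "to the primary physicians and to the nurses in charge at the same clinics". Item 0 and Appendix 4 provide an advance notice to primary physicians, whatever the arm of their patients. On analysis, item 6 says: "Differences between the arms of the study will be examined using Chi-square test". It does not mention spillover between patients of the same clinician.

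The patient table in item 1.A records the clinic and the primary physician, and also "Nurse in charge at the clinic; email address of that nurse".

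**The concern.** A physician or nurse in charge may have eligible patients in both arms. A letter about one patient can change how that clinician treats another. The letters encourage this to some degree: Appendix 2 gives HbA1c levels of 6.5% and 8%, Appendix 3 a cholesterol level of 160 mg%, and the background in Appendix 1 a BMI range of 25-30. The advance notice names all three topics to primary physicians.

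If controls gain part of the benefit, the difference between arms understates the total effect of alerting clinicians. A null mortality result, set against the wording of the Objectives, could then be reported as evidence that reminders do not work. The planning effect adds to the worry. The fall from 3% to 1.8% came from a comparison with matched controls of the previous year, so it is closer to a total effect than to the difference between patients under the same staff.

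**Working it through.** **1. Opportunity for spillover.** With 1:1 coin-flip allocation and m eligible patients per clinician, the chance that a control shares the clinician with at least one alerted patient is 1 − 0.5^(m−1). The documents do not give m, so these values are assumed.

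| m | 2 | 3 | 5 | 10 |
|---|---|---|---|---|
| Chance | 50% | 75% | 94% | 99.8% |

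Sharing a clinician is therefore likely even on short lists. That is opportunity only; it says nothing about how much practice changes.

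**2. The plan's own power.** Item 1.C gives about 10,000 patients, 3% v 1.8% and a Pearson chi-square test. It calls the power sufficient without stating a figure. Two-sided 5% is assumed, since item 6 does not state sidedness. With n = 5,000 per arm and a mean rate of 2.4%:

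- SE under the null = √(2 × 0.024 × 0.976 / 5,000) = 0.003061
- SE under the alternative = √((0.03 × 0.97 + 0.018 × 0.982) / 5,000) = 0.003059
- z = (0.012 − 1.96 × 0.003061) / 0.003059 = 1.96, so power = 97.5%

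For 80% power, 5,106 patients in total are enough. The claim of sufficient power holds for the pooled sample without spillover.

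**3. Power with spillover.** Let controls receive a fraction c of the effect. The control rate becomes 3% − c × 1.2 points, and the letter arm stays at 1.8%.

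| c | Control rate | Power, 5,000 per arm |
|---|---|---|
| 0 | 3.00% | 97.5% |
| 0.10 | 2.88% | 94.7% |
| 0.20 | 2.76% | 89.6% |
| 0.30 | 2.64% | 81.4% |
| 0.50 | 2.40% | 55.3% |

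Pooled power reaches 80% at c = 0.313.

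**4. Power per alert.** Hypothesis 2 refers to each study group, and group sizes are not given. For an assumed group of 5,000 patients, power falls from 79.2% at c = 0 to 62.3% at c = 0.20. For an assumed 3,333 it falls from 61.9% to 45.9%. The low starting values come from group size, which is a separate matter.

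**5. Validity.** If the letters have no effect on anyone, sharing staff does not by itself create a difference between arms. If a benefit spills over, the difference shrinks and a positive result is conservative.

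**6. The alternative design.** Allocation by clinic or physician would target the total effect, at a cost of 1 + (m − 1) × ICC in variance. With assumed clusters of 20 and ICC 0.01 the design effect is 1 + 19 × 0.01 = 1.19, the effective total is 10,000 / 1.19 = 8,403 and power is 94.9%. With clusters of 50 and ICC 0.02 it is 1 + 49 × 0.02 = 1.98, the effective total is about 5,051 and power is 79.6%. Which design does better depends on quantities the documents do not give.

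**The case for a change.** The strongest case for a change is that it would be cheap. One sentence in item 6 could limit the conclusion to the added effect of a patient-specific letter and warn against over-reading a null result. A table of eligible and alerted patients per physician and per nurse would show how many controls were exposed. An exploratory regression among controls, on the share of the same physician's other patients who were alerted, might detect spillover.

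The sentence is accurate if worded moderately: a null result would not by itself prove that reminding clinicians has no effect. To call a null result no evidence at all would go too far when pooled power is still 89.6% at 20% spillover. The sentence also repeats a contrast that the Methodology already sets out, and it alters neither the data nor the test. The table can be made from fields that item 1.A already collects, provided a coded clinician link is kept when identifiers are removed under item 5.

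The regression would add little. In a simulation (3,000 runs per cell) with assumed inputs of 3,333 eligible patients, 85% dispensing, a physician SD of 5 points and a 6-point spillover proportional to the share alerted, its power was 61%, 35%, 17% and 11% at 3, 5, 10 and 20 patients per physician. A yes/no version, comparing controls with and without an alerted co-patient, soon runs out of unexposed physicians. With lists of 5, about 667 × 0.5^5 ≈ 21 physicians would have no alerted patient, and its false-positive rate there was 7.6%. A near-zero estimate would settle nothing.

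The direction of spillover is not certain either. The letters disclose that only intervention patients trigger alerts, so attention could move away from the others and widen the contrast. Staff are not told who the controls are; for alert 1 they would have to notice a two-year BMI drop unaided.

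**Conclusion.** No change to the plan follows. The design estimates the added effect of a letter about a particular patient, among staff who may have had letters about others and physicians who were sent the advance notice. The Methodology and the main hypotheses say as much; only the summary sentence in the Objectives is broader. Allocating by patient under shared staff is a fair trade-off: it keeps a valid comparison and full sample size, and accepts some dilution.

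The size of that dilution is unknown. Pooled mortality power stays above 80% if less than about 31% of the effect reaches controls, and falls to 55.3% at half. This rests on 3% v 1.8%, 5,000 per arm, a two-sided 5% test and benefit-type spillover. Single alert groups have less room, mainly because they are smaller. Careful authors would state the limitation and describe how patients were spread over clinicians when reporting, and the collected fields allow both. The further analyses considered would be too imprecise, except perhaps on very short lists, to improve the conclusion.
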